Specific Aim 2: Determine the safety of insulin glargine 0.4 unit/kg early administration within four hours from IV Insulin infusion initiation.

III. METHODS

A. Study Design and Methodology:

This will be a prospective, open-label, intervention cohort study including all consecutive adult patients with Diabetes Ketoacidosis (DKA) getting admitted to Fairview Hospital-Medical Intensive Care Unit (FV-MICU). Screening of patient eligibility and informed consent will be done by the MICU admitting physician once the patient gets admitted to MICU. Participants will be given an overview of the study, including study procedures, and potential risks. Participants will be given adequate time to review the consent form and have opportunities to ask questions. After the informed consent process has been completed and a consent form has been signed, a copy of the consent will be provided to the participant and another copy will be secured in the Principle Investigator office in a locked cabinet. Enrolled participants in the intervention group will receive an Insulin Glargine 0.4 Unit/kg within 4 hours from initiating the IV Insulin Infusion, as per the Cleveland Clinic DKA protocol. The remaining of the management will be following the CC DKA protocol including continuing IVII till Anion Gap Closure ($AG \leq 12$), Basal Metabolic Panel Q 2 hrs, and replacing electrolytes as indicated. After closing the anion gap, the decision for giving more Basal Insulin doses will be left to the treating physician's discretion. For patient safety, Point Of Care (POC) blood glucose will be checked hourly before IVII discontinuation. After IVII discontinuation, the BG will be checked with meals, bedtime and 2 am if the patient maintain good oral intake, if not, the BG will be checked q 4 hrs. Target BG 150 – 200 mg/dl during the DKA management and 140 – 180 mg/dl after DKA resolution as per American Diabetes Association recommendations. In case of any hypoglycemia event, this goal will be achieved by using Dextrose containing fluid or carbohydrate enriched oral intake which will be left to the treating physician discretion depending on patient awareness and severity of hypoglycemia. Also, the pre meals and correctional insulin doses after AG closure will be left to the treating physician's discretion. After AG closure the pre meals and correctional insulin doses will be left to the treating physician's discretion. In case of not closing the AG after 24 hours from the initial Glargine dose, the decision for further Glargine doses will be left to the treating physician's discretion.

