Transitional failure will be defined as the recurrence of DKA ($BG \geq 250$ mg/dl, $AG > 12$, and positive Ketones in serum or urine) after initial IVII discontinuation within 24 hours and requiring reinitiating the IVII.

C. Study Population

Intervention vs Control group

- Intervention group: All consecutive adult patients getting admitted to FV- MICU and meet the inclusion criteria and accepted to receive insulin glargine early as per the protocol. They will receive insulin glargine 0.4 unit/kg within 4 hours from initiating the IV Insulin Infusion, as per the Cleveland Clinic DKA protocol.
- Control group: prespecified and matched sample size, consecutive adults who admitted to FV-MICU with a diagnosis of DKA in the period between January 1st 2019 till the IRB approval date and didn't receive basal insulin before AG closure.

Inclusion criteria:

- Age \geq 18 years old
- Meet DKA definition as above
- Having the capacity to sign Informed consent

Exclusion Criteria

- IV insulin infusion initiated more than 4 hours.
- Persistent hypotension (SBP<80 mmHg despite receiving 1000cc normal saline).
- Require Vasopressor
- Acute Coronary Syndrome
- Pregnant
- End-stage renal disease
- Unwilling to consent to participate in the trial
- Currently under police custody
- Transferred from another hospital
- Require emergent surgery
- Alcoholic Ketoacidosis

Study Variables:

General Informations:

- Patient name
- MRN
- Age
- Sex (Male, Female, Others)
- Race (White, Black, Asian, Other)
- Ethnicity (Hispanic vs. Non-Hispanic)
- Weight on admission (kg)
- BMI (Kg/m²)
- Height (cm)
- Date of Hospital admission
- Date of ICU admission

- Date of DKA diagnosis (MM/DD/YY)
- Precipitating cause of DKA
 - Noncompliance
 - New-onset
 - Infection
 - Cerebrovascular accident
 - alcohol abuse
 - pancreatitis
 - Drugs
 - Others

Past Medical history

- Type of diabetes:
 - Type 1 DM
 - Type 2 DM
 - Cystic fibrosis-related diabetes
 - Steroid-induced diabetes
 - Other or no clear diagnosis
- Known diagnosis of other major medical comorbidities (CAD, CHF, HTN, COPD, asthma, liver disease, CKD, cancer, other)
- On Renal Replacement Therapy (Y/N)
- Using Basal insulin at home (Yes/No/ unknown)
- If previous point answer is yes check the corresponding insulin type and write the dose: (Glargine, Detemir, Degludec, NPH, Continuous Insulin Pump) (dose: IU)
- Home total basal insulin dose (units)

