- Non-insulin antihyperglycemics taken at home prior to admission, including the type
 - Sulfonylureas
 - Thiazolidinediones
 - Dipeptidyl peptidase-4 (DPP-4) inhibitors
 - Biguanides
 - Glucagon like peptide-1 (GLP-1) analogues
 - Sodium-glucose transport protein 2 (SGLT2) inhibitors
 - Meglitinides
 - Alpha glucosidase inhibitors
 - Amylin analogues
- History of immunosuppression (history of cancer, HIV or auto-immune disease or organ transplant, chronic steroid)

Initial Laboratory values:

- Anion gap (mEq/L)
- Bicarbonate (mEq/L)
- Glucose (mg/dL)
- Beta-Hydroxybutyrate (mmol/L)
- Ketones in the urine (Y/N/Unknown)
- HbA1c %
- Lactate (mmol/L)

Intervention and outcomes:

- IV insulin infusion starting time
- Insulin glargine administration time
- Anion Gap closure time
- IV insulin discontinuation time
- Number of hours of IVII
- Total IV insulin infusion has been given
- Total IV insulin/weight
- Total IV fluid during DKA management
- Date of discharge from ICU
- Date of discharge from hospital
- Hospital Length Of Stay (days)
- ICU LOS (hours)
- Transitional failure (recurrence of DKA)?

Hypoglycemia Events

- Hypoglycemia event within 24 hrs from glargine
- Time of the hypoglycemia
- How many hours after the glargine administration?
- Severity
- How it has been treated

Hyperglycemia Events

- Hyperglycemia Event after IVII discontinuation by 24 hours (Y/N)
- time of the hyperglycemia event
- Severity of hyperglycemia
- How many hours after IVII discontinuation

D. Outcomes

Primary outcome: Time to anion gap closure (hours).

Secondary outcomes:

- Hospital Length of stay (days)
- ICU length of stay (hours)
- Total IV insulin infusion dose (International unit)
- Incidence of transitional failure (percentage).
- Incidence of hyperglycemia (> 180 mg/dL) during 24 hours from Insulin Glargine administration (percentage).
- Incidence of hypoglycemia (defined as ≤ 70 mg/dL, <54, <40) during 24 hours from Insulin Glargine administration (percentage).

IV. DATA COLLECTION

For the control group, the data will be collected retrospectively and recorded in standardized DCS in RedCap. For the intervention group, the data will be collected prospectively by the investigator team members and observations will be recorded in standardized DCS in RedCap. All protected health information (PHI) will be de-identified for both intervention and control group by using de-identification function in REDCap.

V. DATA ANALYSIS

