The sample size calculation considered the average time of AG closure in the last 3 months in FV-MICU was 15.6 ± 2.5 hours (CI 95%) and SD of 6 hours. Using one-sided α of 0.025 and an β of 0.10, an expected 20% difference between the two groups, a sample size of 160 totally of the participant will be adequate.

Categorical variables will be described as frequency rates and percentages, and continuous variables will be described using mean, median, and interquartile range (IQR). Proportions for categorical variables will be compared by Chi-squared test of Fisher's exact test. Means for continuous variables will be compared by Student's t-test if normally distributed and Mann-Whitney test if not normally distributed. All statistical analyses will be performed with a one-sided p-value < 0.025 to determine statistical significance. All statistical analyses will be completed by study investigators using Statistical Analysis Software (SAS).

VI. DATA AND SAFETY MONITORING PLAN (if applicable)

All data will be stored in a secured REDcap database. No PHI will be saved on non-HIPAA protected devices. All protected health information (PHI) will be de-identified by using RedCap.

To ensure patient safety, CCF Hypoglycemia protocol is getting followed in all patients receiving insulin including our enrolled participants. Before IV insulin discontinuation, the blood glucose level is getting checked hourly as per protocol. Once the AG is closed and insulin infusion is discontinued, the patient who is maintaining oral intake, blood glucose will be checked with meals, bedtime, and 2 am. If the patient having poor oral intake, blood glucose will be checked q 4 hours. Different treatment options for any hypoglycemic events are available in the protocol depending on the severity of the hypoglycemia event and patient awareness, ranging from oral carbohydrate supplement to IV fluid containing dextrose.

VII. STUDY LIMITATIONS

- Retrospective EPIC data review for the control group. Single-center.

VIII. ETHICAL CONSIDERATIONS

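### The one-sided significance rule covers hypoglycemia without a direction or an interval, and the 24-hour glargine window puts the two groups in different phases of care

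*Combined protocol and SAP*

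**What the plan says.** Specific Aim 2 (Section II) is to "Determine the safety of insulin glargine 0.4 unit/kg early administration within four hours". Its main measure is a secondary outcome in III.D: "Incidence of hypoglycemia (defined as ≤ 70 mg/dL, <54, <40) during 24 hours from Insulin Glargine administration (percentage". The hyperglycemia outcome in III.D has the same 24-hour anchor.

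For inference, Section V says: "All statistical analyses will be performed with a one-sided p-value < 0.025 to determine statistical significance". Binary outcomes are compared by chi-squared or Fisher's exact test. Their summary is limited to this: "Categorical variables will be described as frequency rates and percentages". No interval for a difference, no margin and no direction is given for hypoglycemia. Only the primary outcome has a direction, faster closure.

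In III.C, controls are past patients who "didn't receive basal insulin before AG closure". The data sheet has a glargine administration time, and it words the safety field as "Hypoglycemia event within 24 hrs from glargine". Its hyperglycemia field is tied to the end of the intravenous insulin infusion instead. It also holds the "IV insulin infusion starting time".

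On monitoring, Section VI says: "Before IV insulin discontinuation, the blood glucose level is getting checked hourly as per protocol". Afterwards, glucose is checked with meals, at bedtime and at 2 am, or every 4 hours if oral intake is poor.

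**The concern.** There are two separate gaps in the safety comparison.

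**Direction and interval.** A one-sided test answers one question, and the plan does not say which. If the direction is carried over from the primary outcome (glargine better), an excess of hypoglycemia cannot reach significance. If the direction is toward harm, a study sized for closure time has little power unless hypoglycemia is common. Percentages and a p-value alone would not show how large an excess the data leave open.

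**Time window.** In the intervention group, the 24 hours start within 4 hours of the insulin infusion, so much of the window falls under hourly checks. A control's window from glargine starts at or after closure and falls mostly under sparse checks. A control given no glargine has no window. The groups would then differ in phase of care and in the number of chances to record a low or high value. This alone could create or hide a difference.

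**Working it through.** **Plan's own figure.** Inputs from Section V: mean 15.6 h, SD 6 h, 20% difference (0.20 × 15.6 = 3.12 h), one-sided alpha 0.025, beta 0.10.

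n per group = 2 × (1.960 + 1.282)² × 6² / 3.12² = 77.7, so 78 per group and 156 in total. This agrees with the stated 160. Two-sided 0.05 uses the same 1.960 and gives the same size.

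**Assumptions for the rest.** There are 80 per group (no ratio is stated) and the matching is ignored. Control hypoglycemia is 3% to 20%, because the documents give no rate for this unit.

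**Power for a doubling, tested toward harm.** With p̄ the mean of p1 and p2:

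power = Φ{ [(p2 − p1) − 1.960 √(2p̄(1 − p̄)/80)] / √([p1(1 − p1) + p2(1 − p2)]/80) }

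For 10% against 20%: (0.10 − 1.960 × 0.0565) / 0.0559 = −0.19, so power is 42%.

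| Control rate | Doubled rate | Power toward harm | Chance of significance toward benefit (exact enumeration) |
|---|---|---|---|
| 3% | 6% | 15% | 0.20% |
| 5% | 10% | 22% | 0.07% |
| 10% | 20% | 42% | 0.009% |
| 20% | 40% | 79% | <0.001% |

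**Two worked results.**
- 20/80 with glargine against 8/80 in controls: one-sided Fisher p is 0.010 toward harm and 0.997 toward benefit. The unstated direction decides the outcome.
- 16/80 against 8/80: z = 0.10 / √(2 × 0.15 × 0.85 / 80) = 1.77, one-sided p = 0.038 toward harm (Fisher 0.060). This is not significant, yet the risk difference is +10 points with a Newcombe 95% interval of −1.2 to +21.2.

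**Window overlap.** Count hours from the start of the infusion. The intervention window runs from 0–24 (glargine at once) to 4–28 (glargine at hour 4). If a control receives glargine at closure, assumed at 15.6 h, the window is 15.6–39.6. Overlap is 24 − 15.6 = 8.4 h to 28 − 15.6 = 12.4 h.

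**Expected readings.** Assume that the Section VI schedule applied to both groups, that the infusion stops at closure, and that closure in the intervention group is 20% faster (12.48 h). Checks are hourly during the infusion, then 5 or 6 a day.
- Intervention, glargine at hour 0: 12.48 + 11.52 × (5 or 6)/24 = 14.9 to 15.4.
- Intervention, glargine at hour 4: 8.48 + 15.52 × (5 or 6)/24 = 11.7 to 12.4.
- Controls from glargine at closure: 5 to 6.
- Controls from infusion start, 24 h: 15.6 + 8.4 × (5 or 6)/24 = 17.4 to 17.7.

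If the infusion runs 2 h past closure in both groups, the figures are 13.3–16.9 for the intervention group against 6.6–7.5 for controls from closure.

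**Illustrative bias with no true difference.** Assume the same risk r per reading in both groups, independent readings, and the same schedule after the infusion. The chance of at least one low value in k readings is 1 − (1 − r)^k.

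| r | Controls from glargine at closure | Controls from infusion start, intervention from glargine |
|---|---|---|
| 0.25% | +1.6 to +2.4 points | −0.6 to −1.4 points |
| 1% | +5.8 to +9.0 points | −2.0 to −4.9 points |

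The sign depends on the control window chosen. With a common 0–28 h window for both groups, expected readings are 15.7–16.4 against 18.2–18.7, which leaves about −0.6 to −2.1 points.

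**Primary outcome, for wording only.** The standard error is 6 × √(2/80) = 0.949 h. With t = 1.975 on 158 degrees of freedom, significance is reached at 1.87 h, or 12% of 15.6 h.

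**The case against.** The strongest reply is that controls do have a time zero. The data sheet serves both groups and lists a glargine time, Aim 1 contrasts early with late administration, and Section VIII describes glargine after closure as usual practice. A reader might infer that the control window is simply absent. The documents do not support that, because each patient's own glargine time is a natural reading. What stands is that this reading gives the mismatched windows shown above, and that III.C does not require a control to have received glargine at all.

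The bias figures rest on an invented risk per reading and on independence, which hourly values in one patient do not have. That is fair. They show that the sign can change, and they do not estimate its size.

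A common window is also imperfect. Hours 0–28 contain the full 24 hours after glargine for the intervention group, but at most 12.4 hours after glargine given to a control at 15.6 h. Low values after a control's later dose would be missed, which tilts the comparison against early glargine. The fix must say so.

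A reader might also infer that one-sided 0.025 is wrong for the primary outcome, or that the plan tests Aim 1's 20% as a minimum. Neither follows. One-sided 0.025 gives the same size as two-sided 0.05, and Section V uses 20% as the expected difference. Nor do the documents say that a non-significant hypoglycemia result will be reported as proof of safety. The plan leaves that inference open, and Section VIII draws a similar one from earlier studies.

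**Conclusion.** The concern holds for the safety outcomes. As written, the hypoglycemia test has either almost no chance of flagging an excess (0.2% or less for a doubling) or, toward harm, power of about 15% to 79% for a doubling from assumed rates of 3% to 20%. These figures assume 80 per group. The comparison also mixes phases of care: 8.4 to 12.4 of 24 hours are shared if controls receive glargine at closure and closure is at 15.6 h. The direction and size of the resulting bias are unknown. The illustration runs from about +1.6 to +9 points under one control window and from about −0.6 to −5 under another. Hyperglycemia shares the window problem, and its data-sheet field uses yet another anchor.

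The primary analysis and the total of 160 are not affected. For Aim 1 the point is wording only: a significant result supports faster closure, not a reduction of 20% or more.

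**What to change.** 1. **Section V.** Do not apply the one-sided rule to safety outcomes. At each hypoglycemia threshold, report n/N per group and the risk difference with a two-sided 95% Newcombe interval. Draw no safety conclusion from non-significance. With 80 per group and equal rates, the half-width is about 7.8 points at 5%, 9.8 at 10% and 12.4 at 20%.
2. **III.D and the data sheet.** Count hypoglycemia and hyperglycemia in both groups over one identical window from the start of the insulin infusion, fixed before control data are extracted. Hours 0–28 are one example. Report the number of glucose readings per patient by group. State that this window covers less time after glargine in controls and leaves somewhat unequal readings. Show 24 hours from each patient's own glargine as a supplementary description.
3. **First threshold.** Use one definition throughout. III.A and III.D include a value of exactly 70 mg/dL, and III.B does not.
4. **Aim 1 wording.** Describe 20% as the effect the study is sized to detect.

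**Cost.** The sample size does not change. Control glucose data must be extracted for the common window, since the present hypoglycemia field is tied to glargine. Aim 2 becomes an estimate with wide intervals.

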
The investigator team will be notified by the MICU attending after each participant enrollment, so one of the team members will present to MICU to collect the data prospectively in a standardized Data Collecting Sheet (DCS) by using REDCap and all protected health information (PHI) will be de-identified. As regards the control group, an E-research request will be submitted to provide a list by

all the consecutive adult patients admitted to FV-MICU with a diagnosis of DKA in the period between January 1st 2019 till the date of IRB approval. Prespecified sample size and matched in basal patient characteristics and DKA severity will be selected as the control group. Data will be collected retrospectively for the control group and will be recorded directly into the DCS in RedCap. Clinical outcomes will be compared between the intervention and control groups. The primary outcome includes time to anion gap closure ($AG \leq 12$). Secondary outcomes include hospital Length Of Stay (LOS), ICU LOS, total IVII dose, the incidence of transitional failure (defined recurrence of DKA after initial IVII discontinuation within 24 hours and requiring reinitiating the IVII), the incidence of hyperglycemia (> 180 mg/dL) and hypoglycemia (defined as ≤ 70 mg/dL, <54 , <40) during 24 hours from Insulin Glargine administration.

B. Definition of main exposures and outcomes:

Diagnosis of DKA will be made by ICD-10-CM code E10.10, E11.10, or meeting the ADA definition; $BG \geq 250$ mg/dl, $AG > 12$, and positive Ketones in serum or urine

DKA classification as the following table from ADA:

	Mild (plasma glucose >250 mg/dl)	Moderate (plasma glucose >250 mg/dl)	Severe (plasma glucose >250 mg/dl)
Arterial pH	7.25–7.30	7.00 to <7.24	<7.00
Serum bicarbonate (mEq/l)	15–18	10 to <15	<10

For the hyperglycemia analysis, patients will be compared in the following categories according to their mean or median (depending on the normality of the data distribution) blood glucose throughout the hospital stay:

- Mean/median BG <80 mg/dL
- Mean/median BG 81-100 mg/dL
- Mean/median BG 101-140 mg/dL
- Mean/median BG 141-180 mg/dL
- Mean/median BG > 180 mg/dL'
- Mean/median BG > 240 mg/dL

Hypoglycemia will be defined by three categories:

- any glucose level below 70 mg/dL
- any glucose level less than 54 mg/dL
- any glucose level less than 40 mg/dL

For Time of Anion Gap Closure (TAGC) will use the ADA definition: $AG \leq 12$ mEq/L

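### The plan lets any secondary outcome be called significant at an unadjusted one-sided 0.025, even if time to anion gap closure fails

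*Combined protocol and SAP*

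**What the plan says.** Section III.D names a single primary outcome: "Primary outcome: Time to anion gap closure (hours", followed by six secondary outcomes. Section III.A gives the same list: "Secondary outcomes include hospital Length Of Stay (LOS), ICU LOS, total IVII dose, the incidence of transitional failure", then hyperglycemia and hypoglycemia. The hypoglycemia item has three cut-offs: "Incidence of hypoglycemia (defined as ≤ 70 mg/dL, <54, <40) during 24 hours".

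Section V sizes the study on the primary outcome alone: "Using one-sided α of 0.025 and an β of 0.10, an expected 20% difference between the two groups". It then names the tests (chi-squared or Fisher's exact for proportions, Student's t or Mann-Whitney for continuous outcomes) and gives one decision rule: "All statistical analyses will be performed with a one-sided p-value < 0.025 to determine statistical significance".

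That is the whole analysis section. Neither it nor any other section gives a testing order, a multiplicity adjustment, a rule that secondary tests wait on the primary, or a statement that secondary results are exploratory or supportive.

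**The concern.** The rule in Section V covers all analyses and says what settles significance, so it is a decision rule for each secondary outcome as well as for the primary. If time to anion gap closure misses 0.025, the plan still permits a claim of significant benefit on whichever secondary outcome crosses that line. Several outcomes give several chances of a spurious success, and the plan does not tell a reader how much weight such a success should carry.

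The temptation is real. The background section argues that two earlier trials without statistically significant results were nevertheless clinically important, and its examples include insulin dose, rebound hyperglycemia and hospital stay. Those are the kinds of outcome that are secondary here.

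**Working it through.** **Step 1. Reproduce the plan's figure.** Inputs from Section V: "FV-MICU was 15.6 ± 2.5 hours (CI 95%) and SD of 6 hours", one-sided α = 0.025, β = 0.10 and a 20% difference, so δ = 0.20 × 15.6 = 3.12 h. No allocation ratio is given; 1:1 is assumed.

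n per group = 2σ²(z₀.₉₇₅ + z₀.₉₀)²/δ² = 2 × 36 × (1.960 + 1.282)²/3.12² = 77.7, so 78 per group and 156 in total. The exact t-test gives 79 per group, 158 in total. Both agree with the stated figure: "a sample size of 160 totally of the participant will be adequate". Power at 80 per group is Φ(3.12/(6√(2/80)) − 1.960) = Φ(1.329) = 90.8%. So 0.025 is the level for one test of one outcome, and the sample size rests on nothing else.

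**Step 2. Define the family.** The stake is a false claim of benefit, so the relevant outcomes are hospital LOS, ICU LOS, total IV insulin dose, transitional failure and hyperglycemia: five tests. Hypoglycemia is left out because it answers the safety question of Specific Aim 2.

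**Step 3. Chance of at least one false positive among the five**, with no true effect on any of them and each tested at one-sided 0.025:

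- Independent: 1 − 0.975⁵ = 0.119.
- Common correlation ρ between test statistics: 1 − ∫ φ(t) Φ((1.960 − √ρ·t)/√(1 − ρ))⁵ dt.

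**Step 4. Chance that the primary fails and at least one of the five succeeds.** This is the probability of any success among six tests (primary plus five) minus the primary's 0.025. It assumes the same ρ throughout and no true effect on any of the six.

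| ρ (assumed) | Any of five | Any of six | Primary fails, at least one of five succeeds |
|---|---|---|---|
| 0 | 11.9% | 14.1% | 11.6% |
| 0.3 | 10.5% | 12.1% | 9.6% |
| 0.5 | 9.1% | 10.3% | 7.8% |
| 0.7 | 7.4% | 8.2% | 5.7% |
| 0.9 | 5.1% | 5.4% | 2.9% |

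**Step 5. Sparse outcomes.** With 80 per group, one-sided Fisher's test at a nominal 0.025 has a true size of about 1.4% at an event rate of 10%, 0.8% at 5% and 0.1% at 2%. These rates are assumptions. If transitional failure occurred in 10% and were tested this way, the independent figure would fall to 1 − 0.975⁴ × (1 − 0.014) = 10.9%.

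**The case against.** The strongest reply is that nothing promised has been broken. The plan names one primary outcome in advance, tests it at 0.025 and sizes the study on it; 0.025 is a per-test level, and no family-wise rate is claimed for the secondary outcomes. This stands. A reader might infer that the study's stated error rate is exceeded several times over, but that sets a family-wise rate against a per-test one. The gap is an omission, not a contradiction.

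A reader might also count eight secondary tests by including the three hypoglycemia tiers, which gives 1 − 0.975⁸ = 18.3% under independence. That figure does not fit the harm. A false signal of excess hypoglycemia would count against glargine, and these are safety outcomes that should not be adjusted in any case. Nor do the glucose categories in Section III.B make a further one-sided test: they are not in the outcome list, and a comparison across categories has no single direction. The plan also does not state a direction for each secondary test, but nothing in it suggests that directions would be chosen after seeing the data, so no figure is attached to that.

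Correlation is a fair objection as well. IV insulin runs until the gap closes, so dose is tied to the primary outcome, and ICU stay is part of hospital stay. The independence figure is therefore an upper-end value.

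Finally, in a single-center study with historical controls, confounding may produce more false secondary findings than multiplicity does. That is true, and it limits what this change can achieve. It does not justify leaving the significance rule open.

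**Conclusion.** The point holds as a minor one. Followed literally, Section V allows a claim of significant benefit on a secondary outcome after a failed primary, with nothing to mark it as supportive. Across the five benefit-type outcomes the chance of at least one false positive is about 12% if independent, 9% at correlation 0.5, 7.5% at 0.7 and 5% at 0.9.

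These figures assume no true effect on any of the five, an equal correlation among the test statistics (the documents give none), and tests that each have a true size of 0.025. Fisher's test on sparse outcomes would lower them; bias from the non-randomized control group is outside them. The documents do not support a conclusion that the primary analysis is compromised: its type I error and the sample size of 160 stand.

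**What to change.** In Section V:

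- Restrict the one-sided 0.025 significance rule to time to anion gap closure.
- Report hospital LOS, ICU LOS, total IV insulin dose, transitional failure and hyperglycemia as between-group differences with 95% confidence intervals, labelled supportive and without significance claims.
- Report each hypoglycemia tier with an unadjusted confidence interval as a safety outcome, so that a possible harm is not hidden by a correction.

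A sponsor that wants formal secondary claims could instead test the five by Holm's procedure, and only if the primary is significant. This is optional and more open to debate. The primary should not be put into a plain Bonferroni family: with six tests the level would be 0.025/6 = 0.0042, and primary power at 80 per group would fall from about 91% to about 74%.

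The recommended change costs a few sentences, no patients and no primary power. Its downside is that fewer secondary results can be called significant. It does not address confounding from the historical control, which needs separate handling.
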